## 7.5 6 weeks post-op

All patient participants will be reviewed in a routine outpatient clinic at 6 weeks postoperatively (from date of surgery). Please also see section 7.12 on contingency planning.

PROMS questionnaires to be completed are listed below. The Oxford Hip Score is to be completed first, others are shown in a recommended order of completion of most recent recall period:

- Oxford Hip Score
- EQ-5D-5L™
- Self-Administered Patient Satisfaction scale
- Forgotten Joint Score
- Work Productivity and Activity Impairment—Specific Health Problem

Data will also be collected Adverse Events of Special Interest; these will primarily be surgical complications, such as but not limited to returns to theatre for dislocation, fracture or wound problems; any prescriptions for antibiotics will be noted and any unanticipated contact with the surgical team or GP regarding the surgery.

The earliest this visit can occur is 3 weeks postop and the latest is 12 weeks postop from the date of surgery. Visits outside of these parameters will be recorded as protocol deviations but will not affect the patients continuing participation in the trial.

Every effort should be made to meet the patient in person during the visit. Should this not be possible the questionnaires should be posted as soon as possible to the patient for their completion. Details on how and when to return the questionnaires are included within the covering letter. (See also section 7.7 Loss to follow-up.)

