## 7.6 3-6 month post-op

Patient participants will be required to complete their PROMS questionnaires and healthcare resource use survey between 3 and 6 months postoperatively (from date of

**IRAS Ref: 271885** Page 40 of 89

surgery). This follow-up period will be dictated by the remaining duration of the study. All patient participation activity is expected to be completed by the end of October 20201. See the table below.

Month of Operation	Follow-up time point	Follow-up duration
January '21	July '21	6 months
February '21	August '21	6 months
March '21	September '21	6 months
April '21	October '21	6 months
May '21	October '21	5 months
June '21	October '21	4 months
July '21	October '21	3 months

PROMS questionnaires and a healthcare resource use survey will be sent in the post for the patient participant to complete. The accompanying cover letter will advise that the Oxford Hip Score is to be completed first, others are shown in a recommended order of completion of most recent recall period:

- Oxford Hip Score
- EQ-5D-5LTM
- Self-Administered Patient Satisfaction scale
- Forgotten Joint Score
- Work Productivity and Activity Impairment-Specific Health Problem
- Healthcare Resource Use Survey

A member of the hospital research team will contact the patient participants by phone before distribution to inform them of the upcoming postal questionnaires. The questionnaires should be posted early enough that the patient participant is in possession of them at the required 3-6 month post-operative date.

Patient participants will also be asked about any return to theatre required and any unanticipated contact with the surgical team or GP regarding the surgery.

The earliest that this data can be collected is 4 months postoperatively and the latest time is 8 months. Completion of these questionnaires outside of these parameters will be recorded as protocol deviations but will not affect the patients continuing participation in the trial.

Details on how and when to return the questionnaires are included within the covering letter.

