## 7.11 Quality of Life and Health Economics

Health Related Quality of Life and Health Economics outcomes measures

Health-related quality-of-life (HRQL) and other outcomes for use in the health
economics component of the study will be assessed using the following
questionnaires:

- Oxford Hip Score (OHS)
- EuroQol 5 Dimension, 5 Level Quality of Life Questionnaire (EQ-5D-5L™)
- Self-administered Patient Satisfaction scale (SAPS)
- Forgotten Joint Score (FJS)
- Work Productivity and Activity Impairment-Specific Health Problem (WPAI-SHP)
- Healthcare Resource Use Survey

Baseline data will be collected prior to the patient participant being randomised, with further collections at 6 weeks and 3-6 months post-operation. The only exclusions to this are the Health Resource Use Survey data, which is only collected at baseline and 3-6 months post-operation and SAPS data, which is not collected at baseline and will only be collected at 6 weeks and 3-6 months post-operation.

- The Oxford Hip Score© is used to assess joint-specific pain and functional limitations encountered by the patient participant in day-to-day activities over the preceding 4 weeks.
- EQ-5D-5L™ is a preference-based HRQL measure comprising five domains, each with five levels. HRQL scores can be attached to each of the possible 3125 health states it describes.
- Self-administered Patient Satisfaction scale is a tool to measure patient satisfaction with their operation, pain, and ability to do daily activities and recreational activities.
- The Forgotten Joint Score is a 12 question scale used to measure joint awareness. It has been extensively validated to assess outcomes after total hip arthroplasty.
- Work Productivity and Activity Impairment-Specific Health Problem records data on work time and productivity over the preceding 7 days.
- The Healthcare Resource Use Survey is a HipHOP specific questionnaire

**IRAS Ref: 271885** Page 44 of 89

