#### 10.2 Outcomes

The National Institute for Health and Care Excellence (NICE) recommends economic evaluations apply cost-utility analysis (CUA) to assess the costs and consequences of healthcare interventions. In a CUA, quality-adjusted life years (QALYs) are used as the primary outcome which capture the quality and quantity of life in a single measure. A QALY is calculated by multiplying the quality of life by the quantity of life. The quantity of life is measured using a count of the number of life years. Quality is measured using preference-weighted surveys such as the EuroQol 5 Dimensions 5 levels (EQ-5D-5LTM). The EQ-5D-5LTM provides a simple descriptive profile and a single index value for health status with an associated utility tariff. Utility values will be calculated for participants and will be used to estimate Quality Adjusted Life Years (QALYs) as a measure of health benefit. Total QALYs will be estimated as follows:

$$QALY = \Sigma[(U_i + U_i + 1)/2] \times (t_i + 1 - t_i)$$

Here, U = utility value and t = time between assessments. The time between assessments is the time from baseline data collection to follow-up, i.e. 3-6 months. Patients will be asked to complete the EQ-5D-5LTM survey at baseline and between three and six months follow-up.

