## 11.2.2 Secondary

- 1. Adherence to the protocol will be measured by:
  - i. the number of minor (e.g. visit time-point violation) or major (e.g. violation of inclusion criteria) protocol deviations collected on a patient participant and site level. (The definitions of minor and major protocol deviations will be in accordance with LCTC categorisations that will be allocated to each deviation by the CI after assessment of the details)
  - ii. the percentage of patients in each arm that were accidentally unblinded
- 2. Trial withdrawal rate at 6 weeks and 3-6 months will be measured using the total number of patients randomised in the study. In addition, withdrawal rates will be presented by trial withdrawal reasons and withdrawal stage for both arms.
- 3. Patient participant population characteristics will be measured by collecting the following information:
  - i. Age
  - ii. BMI
  - iii. Proportion of missing data
  - iv. Loss to follow up
- 4. Clinical and patient reported data will be measured by collecting the following information:
  - i. Patient participant-reported outcomes including change in OHS, FJS, WPAI-SHP, SAPS score and quality of life measured using the EQ-5D-5L™ at 6 weeks and 3-6 months
  - ii. Revision rate, defined as the number of patient participants needing Revision arthroplasty within 3-6 months of surgery
  - iii. Infection rate, measured as the rate of re-operation for infection within 3-6 months of surgery
  - iv. Length of stay, measured in hours
  - v. Operation time, measured in minutes

**IRAS Ref: 271885** Page 50 of 89

- vi. Incidence of treatment cross over during surgery
- vii. Incidence of intra-operative surgical complications, the proportion of patient participants experiencing greater than grade III severity will be measured and reported according to Clavien Dindo classification system^24.
- viii. Incidence of postoperative surgical complications, the proportion of patient participants experiencing greater than grade III severity will be measured and reported according to Clavien Dindo classification system^24.
- 5. Completeness of the EQ-5D-5L™ and Healthcare Resource Use Survey will be measured by using the follow methods:
  - i. Descriptive statistics will be used to assess the frequency of missing data for the EQ-5D-5L™ and Healthcare Resource Use Survey.
  - ii. Any patterns in missing data will be identified through the use of descriptive statistics

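### Section 10.2 leaves the 6-week EQ-5D-5L out of the QALY, although four other sections of the protocol collect it

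*Protocol*

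**What the plan says.** Section 10.2 introduces an area-under-the-curve formula with the words "Total QALYs will be estimated as follows". The formula is a sum over successive pairs of assessments, so it can take any number of time points. The text below it then fixes a single interval: "The time between assessments is the time from baseline data collection to follow-up, i.e. 3-6 months". It adds that patients complete the EQ-5D-5L "survey at baseline and between three and six months follow-up". The 6-week assessment is not mentioned.

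Four other places say otherwise:

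- Section 7.5 lists the EQ-5D-5L among the questionnaires for the 6-week visit ("All patient participants will be reviewed in a routine outpatient clinic at 6 weeks postoperatively").
- Table B in section 7.8 marks it at baseline, 6 weeks and 3-6 months.
- Section 7.11 has baseline data with "further collections at 6 weeks and 3-6 months post-operation". It then limits the exceptions: "The only exclusions to this are the Health Resource Use Survey data, which is only collected at baseline and 3-6 months post-operation", plus the satisfaction scale, which is not collected at baseline. The EQ-5D-5L is not among them.
- Section 11.2.2 (item 4.i) makes quality of life on the EQ-5D-5L a secondary outcome "at 6 weeks and 3-6 months".

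Section 10.5 uses the QALYs for an indicative cost per QALY for each implant type and says that the results will not be definitive. It also asks whether the chosen follow-up periods are right to capture changes in health status.

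**The concern.** Section 10.2 contradicts the assessment schedule, and the contradiction affects a calculation. This is not a detail left open for the separate analysis plan. Section 10.2 positively states a two-point rule, so an analyst who used the 6-week utility would depart from the protocol, and one who followed 10.2 would leave a collected value out of the QALY.

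Under the two-point rule, each patient's utility is assumed to move in a straight line from before surgery to the final assessment. Departure from that line is what the 6-week form could show. The effect also scales with follow-up length, which section 7.6 lets vary from 3 to 6 months according to the month of operation. The size of any error would therefore differ between patients for administrative reasons.

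What is at stake is the QALY in the indicative cost per QALY, and the economic aim of judging whether the follow-up periods capture change. A QALY method that ignores one of the two follow-up points cannot show what that point adds.

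**Working it through.** The protocol states no QALY, utility or standard deviation, so there is no figure of its own to reproduce. The check applies the section 10.2 formula with one interval and with two.

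**Inputs**

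- Final follow-up T = 0.25 to 0.50 years, from section 7.6 ("healthcare resource use survey between 3 and 6 months postoperatively").
- Time of the middle assessment s = 6/52 = 0.1154 years (section 7.5, nominal).
- Utilities U0 (baseline), U1 (6 weeks), U2 (final): **assumed**. U0 = 0.35 and U2 = 0.80, with U1 varied from 0.45 to 0.75. For simplicity, baseline is placed at surgery.

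**Formulas**

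- Two-point: (U0 + U2)/2 × T
- Three-point: (U0 + U1)/2 × s + (U1 + U2)/2 × (T − s)
- Three-point minus two-point = (T/2) × (U1 − L), where L = U0 + (U2 − U0) × s/T is the 6-week value on the straight line.

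**One case in full** (T = 0.25, U1 = 0.45)

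- Two-point: 1.15/2 × 0.25 = 0.1437.
- Three-point: 0.40 × 0.1154 + 0.625 × 0.1346 = 0.0462 + 0.0841 = 0.1303.
- By the identity: L = 0.35 + 0.45 × 0.1154/0.25 = 0.558, and 0.125 × (0.45 − 0.558) = −0.0135, which agrees.

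**Range** (difference = three-point minus two-point; % of the three-point value)

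| T (years) | U1 | Two-point | Three-point | Difference |
|---|---|---|---|---|
| 0.25 | 0.45 | 0.1437 | 0.1303 | −0.0135 (−10.3%) |
| 0.25 | 0.60 | 0.1437 | 0.1490 | +0.0053 (+3.5%) |
| 0.25 | 0.75 | 0.1437 | 0.1678 | +0.0240 (+14.3%) |
| 0.50 | 0.45 | 0.2875 | 0.2865 | −0.0010 (−0.3%) |
| 0.50 | 0.60 | 0.2875 | 0.3240 | +0.0365 (+11.3%) |
| 0.50 | 0.75 | 0.2875 | 0.3615 | +0.0740 (+20.5%) |

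The two rules agree only when U1 lies on the line. The sign can go either way, and the gap nearly vanishes in one case.

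**Between-arm difference d at 6 weeks**

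- Gone by final follow-up: the three-point rule counts d × T/2 and the two-point rule counts 0. For d = 0.05 the three-point value is 0.0063 QALY at T = 0.25 and 0.0125 at T = 0.50.
- Half persisting, d = 0.10: the three-point rule counts d × T/2 + (d/2) × (T − s)/2, which is 0.0159 at T = 0.25 and 0.0346 at T = 0.50. The two-point rule counts (d/2) × T/2, which is 0.0063 (0.00625 unrounded) and 0.0125. It captures about 39% and 36% of the difference.

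**The interval itself.** Section 7.6 counts 3-6 months from surgery, but 10.2 counts from baseline. The note in section 7.2 appears to have lost a negative. Read in the light of the matching 56-day consent rule in section 6.2, it lets baseline precede surgery by up to 8 weeks. The span from baseline could then reach about 4.8 months (3 months + 8 weeks) to 7.8 months (6 months + 8 weeks).

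**The case against.** The strongest case on the other side is that little turns on this. Section 10.1 makes the main economic focus a critique of data collection. Section 10.5 disclaims any definitive cost-effectiveness result, and section 11.5 rules out formal comparison of efficacy, cost or safety between arms. The stop/go rule does not use QALYs. No data are lost, and the summation already accepts a third point. All of this stands, and it limits the weight of the point.

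Three stronger readings are tempting, and the documents do not support them:

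- *Any early difference between implants is set to zero.* A reader might infer this, but it holds only for a difference that has gone by 3-6 months. One that partly persists is partly counted. Early differences also remain visible in the 6-week EQ-5D-5L results reported under section 11.2.2.
- *The QALYs are known to be biased, and in a known direction.* The protocol gives no utilities, and the sign changes across plausible profiles. The three-point value is itself an interpolation, and section 7.5 allows the 6-week visit anywhere from 3 to 12 weeks.
- *Adding the 6-week point cuts QALY noise about fourfold.* With an assumed SD of 0.25 and 20 patients per arm, the SE of a baseline difference is 0.25 × √(2/20) = 0.079. At T = 0.50 the baseline term falls from 0.079 × 0.25 = 0.020 to 0.079 × 0.058 = 0.005. But that weight moves to the 6-week utility, which has its own sampling error. With equal SDs and a common correlation of 0 to 0.7, the SE of the whole between-arm QALY difference goes only from 0.028–0.036 to 0.025–0.036. A transient difference worth 0.0125 QALY would be about half an SE or less in this trial.

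What survives is the contradiction and its arithmetic consequence.

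**Conclusion.** The point holds in a limited form. Section 10.2 conflicts with sections 7.5, 7.8, 7.11 and 11.2.2 and, as written, gives a collected utility no weight in the QALY. The consequence, (T/2) × (U1 − L), follows from the formula and needs no assumption beyond the trapezium rule. Its size does need assumptions: −0.0135 to +0.0740 QALY (−10.3% to +20.5% of the three-point value) for baseline 0.35, final 0.80 and a 6-week utility of 0.45 to 0.75. Other utilities would give other figures, and the direction cannot be fixed from the protocol.

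The effect is confined to the indicative cost per QALY and to the aim of judging the follow-up periods. Recruitment outcomes, safety and the stop/go decision are untouched. It should be fixed because the correction is nearly free, but the trial's main conclusions do not depend on it.

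**What to change.** In section 10.2, replace the two sentences below the formula so that they:

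1. Name baseline, 6 weeks and 3-6 months as the EQ-5D-5L time points, in line with section 7.11.
2. Apply the existing summation over the two resulting intervals, with each interval measured between actual assessment dates. This also removes the inexact equation of the baseline-to-follow-up span with 3-6 months.
3. Keep the two-point calculation as a sensitivity analysis, and use it for patients whose 6-week form is missing, with their number reported by arm.
4. Show any between-arm QALY difference adjusted for baseline utility as well as unadjusted.

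The cost is a short text change and no extra data collection, because the forms are already scheduled. The one small drawback is the handling of missing 6-week forms, since patients without one would have a QALY from a different rule. Reporting both calculations would show whether that matters.

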#### 10.3 Costs

It is understood that the fully cemented total hip arthroplasty is less expensive than the hybrid total hip arthroplasty; this may prove to be a key determinant in the cost-effectiveness of each hip replacement procedure. At present, the NHS tariff, which lists the price paid to hospital for performing certain procedures, groups both hip interventions under the same tariff (price). However, to capture the variation in the costs, the cost of each hip replacement procedures will be collected from Wrightington, Wigan and Leigh Teaching Hospitals NHS Foundation Trust procurement department and used in the analysis.

## 10.4 Healthcare Resource use

NICE recommend economic evaluations adopt a healthcare system perspective, therefore only those costs that impact the healthcare sector should be considered and is also in line with a recently published cost-effectiveness analysis of alternative

**IRAS Ref: 271885** Page 48 of 89

prosthetic implants for total hip replacements. A bespoke healthcare resource use survey has been designed to ask patients to self-report their use of healthcare services and resources at baseline (for the previous 6 months) and then again at 3-6 months follow-up. The questionnaire asks patients to consider their use of the following NHS services and/or resources: inpatient stay, outpatient appointment, one-day appointment, accident and emergency services, primary care, community-based services including occupational therapists, and medications prescribed.

These data will be combined with those collected by the scrub team on the day of surgery.

## 10.5 Analysis

A descriptive analysis of the costs and outcomes data will be completed focusing on the extent to which:

- 1. The EQ-5D-5L™ is able to adequately capture differences in health status before and after the hip replacement procedure and across both treatment arms of the study;
- 2. The resource use survey is able to record data necessary to enable a full cost-effectiveness analysis of the two hip interventions;
- 3. The follow-up periods specified are correct to capture changes in health status and healthcare resource use; and
- 4. There is a pattern or random missing data for both the EQ-5D-5LTM and resource-use survey to assess responses, sensitivity, and patterns within the missing data; particularly for resource-use surveys where missing data is a common issue.

Descriptive statistics will also report baseline patient characteristics, retention of participants and return rates for the EQ-5D-5L™ and healthcare resource use surveys. A within-trial analysis will also be conducted to estimate an indicative cost per QALY for each hip replacement intervention. The base-case analysis will use the NHS tariff for each hip replacement intervention. However, in the knowledge that the hip replacement procedures do not cost the same amount, a secondary analysis will be conducted to estimate an indicative cost per QALY using the differential costs for each hip replacement.

Given this is a feasibility study, it must be emphasised that the cost per QALY results from this analysis serve as an indication of the potential cost-effectiveness of the hip replacement procedures. The results will not provide definitive evidence on the cost-effectiveness of the interventions.

**IRAS Ref: 271885** Page 49 of 89

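### The planned cost per QALY for each implant does not show whether the dearer implant's extra cost is justified by extra QALYs

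*Protocol*

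**What the plan says.** Protocol section 10.5 makes the economic work mainly descriptive and then adds one quantitative output: "A within-trial analysis will also be conducted to estimate an indicative cost per QALY for each hip replacement intervention". Two versions are planned. In the first, "The base-case analysis will use the NHS tariff for each hip replacement intervention". In the second, "a secondary analysis will be conducted to estimate an indicative cost per QALY using the differential costs for each hip replacement". The same section says that the figures "serve as an indication of the potential cost-effectiveness of the hip replacement procedures", with the limit that "The results will not provide definitive evidence on the cost-effectiveness of the interventions".

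Other sections set the context:

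- Section 10.3 says that one NHS tariff covers both procedures and that the cemented implant is understood to be cheaper. It gives no amount.
- Section 10.2 calculates QALYs by the trapezium rule: "The time between assessments is the time from baseline data collection to follow-up, i.e. 3-6 months".
- Section 7.6 ties each patient's follow-up to the operation month: 6 months for January to April, then 5, 4 and 3 months for May, June and July.
- Section 11.5 says that costs will not be formally assessed between arms.

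The protocol nowhere mentions an incremental cost, an incremental QALY, an incremental ratio or net benefit.

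**The concern.** A cost per QALY for one implant divides that arm's mean cost by its mean QALYs. This implicitly compares the implant with no cost and no QALYs, which is not an option in the trial. Whether hybrid is worth its price against cemented depends on the cost difference and the QALY difference. Two averages placed side by side do not give that answer, because the large cost and QALY total common to both arms dominate each ratio.

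Secondary objective 7 is to find out whether a within-trial cost-utility analysis is feasible. Averages for each arm do not rehearse the analysis that a full trial would need. A reader told that they indicate cost-effectiveness may take two similar figures to mean similar value for money.

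**Working it through.** The protocol contains no cost, utility or cost-per-QALY figure, so there is nothing of its own to reproduce. All monetary and utility inputs below are assumptions.

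**Formulas.** Average ratio = C / Q in each arm. Incremental ratio = (C_hyb − C_cem) / (Q_hyb − Q_cem). For one interval, section 10.2 gives Q = (U0 + U1)/2 × T.

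**Simple example.** Cemented £6,000 and 0.300 QALY; hybrid £6,500 and 0.305 QALY.

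- Cemented average: 6,000 / 0.300 = £20,000
- Hybrid average: 6,500 / 0.305 = £21,311
- Incremental: 500 / 0.005 = £100,000

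The hybrid average is a weighted mean of the cemented average and the incremental ratio, with weights 0.300/0.305 and 0.005/0.305. The incremental ratio therefore carries a weight of only about 1.6%, which is why the averages barely reflect it.

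**Range.** Cemented cost £6,000, utility 0.35 at baseline and 0.80 at follow-up, T = 0.5 year, so Q_cem = 0.2875 and the cemented average is £20,870. For hybrid, the extra cost was varied from £300 to £1,000 and the gain in follow-up utility from 0.01 to 0.06. The middle case and the two extremes are:

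| Extra cost | Utility gain | Hybrid average | Incremental ratio |
|---|---|---|---|
| £300 | 0.06 | £20,826 | £20,000 |
| £500 | 0.02 | £22,222 | £100,000 |
| £1,000 | 0.01 | £24,138 | £400,000 |

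The hybrid average moves by a factor of about 1.16 while the incremental ratio moves by a factor of 20.

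**Base case.** With a shared tariff the procedure cost difference is zero. If other resource use is also equal, £6,000 / 0.300 = £20,000 and £6,000 / 0.305 = £19,672. The lower average then correctly belongs to the arm with more QALYs. The masking shown above needs a cost difference, so it belongs mainly to the secondary analysis.

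**Follow-up length.** With a mainly up-front cost, halving T doubles the average ratio. On the inputs above, cemented gives £20,870 at 6 months and £41,739 at 3 months. The incremental ratio does the same: in the £500 and 0.02 case it is £100,000 at 6 months and 500 / 0.0025 = £200,000 at 3 months. If one arm has 20 patients at 6 months and an otherwise identical arm has 14 at 6 months and 6 at 3 months, the second arm's mean QALY is (14 × 0.2875 + 6 × 0.14375) / 20 = 0.2444. The averages are then £20,870 and £24,552, an 18% gap from timing alone.

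**The case against.** The strongest reply is that this is a 40-patient feasibility study that has already limited its claims. Section 2.1 says that it will not run a full health economic analysis, section 10.1 puts the main focus on how well the data collection works, section 11.5 excludes formal cost assessment between arms, and section 10.5 calls the figure indicative. All of this stands, and it keeps the point modest. It does not remove it: the label concerns how firm the result is, whereas the difficulty is that an average ratio is the wrong quantity for comparing two implants. Reporting differences descriptively is compatible with section 11.5.

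A reader might also draw stronger conclusions that the documents do not support:

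- *That the figure could distort the decision on a full trial.* Section 11.5 bases progression on recruitment (at least 32, 20 to 31, at most 19 patients) and on the absence of serious problems with randomisation, retention or deviations. Cost per QALY is not a criterion.
- *That dependence on follow-up length is a fault of average ratios.* It affects incremental ratios equally and comes from the variable follow-up. Randomisation in permuted blocks by site should keep operation month roughly balanced, so the 18% gap needs a chance imbalance.
- *That cutting everyone at 3 months would solve this with the same data.* Patients operated on from January to April have no scheduled 3-month EQ-5D-5L, so utilities would have to be interpolated. Resource use comes from a single follow-up survey, and the protocol describes no dating of items that would let it be cut at 3 months.

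**Conclusion.** The point holds for the quantity reported. As written, the plan yields one average cost per QALY for each implant, in both the base case and the secondary analysis, and such averages cannot indicate the cost-effectiveness of one implant against the other. On assumed inputs, averages about 6% apart correspond to £100,000 per extra QALY, and across the range tried the incremental ratio runs from £20,000 to £400,000 while the hybrid average stays between £20,826 and £24,138. These figures show the mechanism. They do not predict the trial's result.

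The consequence is limited to how the economic result is read and reported, mainly in the secondary analysis. The variable follow-up is a separate matter, which changing to an incremental result does not cure.

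**What to change.** In section 10.5, replace the cost per QALY for each implant with mean cost and mean QALYs by arm and their differences (hybrid minus cemented), with bootstrap intervals and with QALYs adjusted for baseline utility. Do this under both the tariff and the differing implant costs. Net benefit at a stated threshold may be added. It is steadier than an incremental ratio, which is unstable when the QALY difference may be near zero. Keep the indicative label and the statement that no formal cost comparison is made.

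Separately, report follow-up length by arm and account for it, for example by including it as a covariate when estimating the QALY and cost differences. If a common 3-month horizon is preferred, state the interpolation and resource-use assumptions that it needs.

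The cost is analysis wording and a little programming, with no new data collection. The drawback is that with 40 patients the intervals will be very wide, and adjustment uses some of the little information available. The width does show honestly how little 40 patients can say about cost-effectiveness.
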